### **2.5.1 PRIMARY PREVENTION**

Primary prevention strategies are important in identifying factors that increase the risk of OA and to prevent OA from occurring. Risk factors such as gender, age, overweight, nutritional factors, occupational factors, sports participation and quadriceps weakness have been shown to play an important role in the development and progression of OA. Some of these risk factors provide a viable approach for reducing the progression and symptoms of OA. The Centers for Disease Control and Prevention and the Arthritis Foundation (2010) highlighted the importance of injury prevention, weight management and healthy nutrition which are able to prevent disease, injury or disability, or to promote health in a group of persons that without OA.

Being overweight was the single most important potentially modifiable risk factor for development of lower limb osteoarthritis. It was also proven to reduce the risk of symptomatic knee osteoarthritis (Felson, 1992). Higher body mass index (BMI) is not only a major risk factor for diabetes, cardiovascular disease, cancer and premature death but is also implicated as a cause of OA, particularly of the knee (Felson, 1990). Murphy, Schwartz, Helmick, Renner, Tudor, ... and Jordan (2008) identified that person who maintain an ideal weight will not easily to develop symptomatic knee OA as they grow older.

Weight loss among people with knee OA has been shown to improve in physical function, self-reported disability, pain symptoms and quality of life. Overweight and obese adults with knee OA who lose one pound gain a four-fold reduction in knee joint load (Messier, Gutekunst, Davis & DeVita, 2005).

In a case control study, they found that patients with OA were 3.5 times more likely than controls who are obese at the age of 20 (Kohatsu et al., 1990). Women who lost 11 pounds decreased their risk for knee OA by 50% (Felson et al., 1992). The other study done by Willims et al. (1981) showed that weight loss resulted in significant reduction of symptomatic OA. Thus, weight loss in overweight patients with OA can have a beneficial effect on the symptoms and progression of the disease. Weight management as primary prevention strategy for the prevention and treatment of OA is underscore the potential public health importance.

Traumatic injury is one of the risk factor for the later development of OA. It contributes 12% of total OA prevalence (Brown, Johnston, Saltzman, Marsh & Buckwalter, 2006). The injuries such as anterior cruciate ligament (ACL) ruptures and ankle fractures are related to the incident of OA (Valderrabano, Hintermann, Horisberger & Fung, 2006). Balance training and other forms of dynamic exercise have been shown to reduce the frequency and rate of falling among older adults. Therefore, it is important to include in the components of a comprehensive physical activity program for older adults (Gillespie, Robertson, Gillerpie, Lamb & Gates, 2009).

### **2.5.2 SECONDARY PREVENTION**

Secondary prevention aims to assure early diagnosis and treatment of OA, even before a person has been diagnosed with symptomatic OA. Therefore, effective interventions are undertaken to minimize the health consequences of the disease.

### **2.5.3 TERTIARY PREVENTION**

Once a person has been diagnosed with OA, tertiary prevention strategies aim to reduce the complications of the disease, such as reducing pain and functional disability, and improving quality of life. Self- management program such as weight control, physical activity and education, cognitive behavioural therapy interventions, rehabilitation services, medical management, and surgical treatments are recommended according to the anatomical distribution, the phase and the progression rate of the disease. Hunter and Felson (2006) have recommended the hierarchy of OA treatment based on the severity of OA symptoms, (1) Non-pharmacological management including education, exercise, weight loss, appropriate footwear; (2) Non- pharmacological management including physiotherapy, braces, and begin pharmacological with simple analgesics such as paracetamol; (3) pharmacological management including NSAIDS, opioids, and aspirate are inject if effusion is present; and (4) Surgery including osteotomy, total joint replacement.

### **2.5.3.1 NON- PHARMOCOLOGICAL MANAGEMENT**

#### **2.5.3.1a SELF- MANAGEMENT PROGRAM**

Education is important for patients with knee OA. The arthritis self- management program, a community educational program in United States reported improvement in level of physical activity, better cognitive pain management and decreased in pain (Lorig, 1981). However, meta-analysis evidences suggests only weak effect of health education on pain and functional limitation.(Warsi, 2003).

Coleman, Briffa, Conroy, Prince, Carroll and McQuade (2008) examined that education program showed significant improvement in knee pain, knee stiffness, physical function of the knee and health- related quality of life over 12-months follow up amongst 79 patients (mean age of 66 years) with knee OA based on the diagnosis by the patients' medical practitioner.

There were few studies on the effectiveness of psychological interventions on knee osteoarthritis pain, pain- related disability and psychological factors, including emotions (e.g. depression, anxiety, psychological distress), cognitions (e.g. self-efficacy for pain control, helplessness, pain catastrophising, pain acceptance, resilient coping) and social context (e.g. pain-related social interactions, pain communication, social support) variables. Emery et al. (2006) have shown that coping skills training (CST) which is one of the psychological intervention had significantly increased nociceptive flexion reflex (NFR) among knee osteoarthritis patients ( $F(1, 60) = 16.19, p < 0.001$ ). A randomized controlled study on the effectiveness of spouse- assisted coping skills training and exercise training in patients with osteoarthritis of the knee showed significant improvements in self-efficacy as compared to exercise training alone or standard care alone ( $F(3, 57) = 4.37, p = 0.008$ ) (Keefe et al., 2004).

A recent study on the effectiveness of group cognitive behavioural therapy intervention among knee osteoarthritis patients was studied to reduce maladaptive pain coping and to increase self- management of knee osteoarthritis pain and arthritis- related disability (Helminen, Sinikallio, Valjakka, Väisänen-Rouvali, & Arokoski, 2013).

#### **2.5.3.1b PHYSICAL AND OCCUPATIONAL THERAPY/ AEROBIC AND MUSCLE-STRENGTHENING EXERCISES**

A randomized controlled trial on the effectiveness of manual physical therapy and exercise in patients with osteoarthritis of the knee showed significant improvement in reducing knee pain, stiffness, and physical disability function, and enhancing walking distance (Deyle, Henderson, Matekel, Ryder, Garber & Allison, 2000).

Perlman, Ali, Njike, Hom, Davidi, ... and Katz (2012) done a study on 125 patients with knee OA based on radiographic evidence of American College of Rheumatology criteria. The intervention group received an eight weeks of Swedish massage (30 or

60 minute weekly or biweekly). Results showed improvement knee pain and functionality in the 60- minute (once weekly) massage groups over six- months follow- up.

A Malaysian study on the effectiveness of passive joint mobilization has shown significant reduction in knee pain among 22 patients (mean age of 61.4 years) with sub- acute or chronic OA (based on clinically and radiographically evidence) (Azlin & Lyn, 2011).

Therapeutic exercise program can improve the functional ability and pain knee OA (Ytterberg, 1994) Although the exact exercise intensity best for OA patients still remained unclear, aerobic and muscle- strengthening exercises generally was consider the core aspect in management of OA patients (Roddy, 2005).

Transcutaneous electrical nerve stimulation (TENS) is the most commonly used form of electro analgesia in the treatment of early arthritis pain in the knee. Clinically TENS is applied at varying frequencies, intensities, and pulse durations of stimulation. When high-frequency TENS is applied at low intensity it is referred to as conventional TENS. The analgesic effect is immediate. Pain relief lasts while the stimulus is turned on, but it usually abates when the stimulation stops.

In contrast, when low-frequency TENS is applied at high intensity so that a motor contraction is produced, it is referred to as acupuncture-like TENS (AL-TENS). Although this method may be more effective than conventional TENS, it is uncomfortable, and many patients do not tolerate it. The mechanism of the analgesia produced by TENS is best explained by the gate control theory of pain. A Cochrane review (2000) of seven studies (148 patients received TENS and 146 patients received placebo treatment) concluded that active TENS and AL-TENS treatment for at least 4 weeks effectively reduce pain and knee stiffness (Osiri et al., 2000).

Electromagnetic fields (EMF) have been postulated as a treatment for early OA since their use has stimulated cartilage growth in vitro. EMF causes physical stress on bone leading to the generation of piezoelectc potentials. These then act as transduction signals to promote bone formation and stimulates chondrocytes to increase proteoglycan synthesis. A Cochrane review (2002) by Hulme et al. (2002) investigating the clinical use of EMF showed statistically significant improvements in function and pain in OA, but it remained unclear as to whether this improvement was noticeable clinically. There are no reported side effects of this therapy.

Ultrasound uses mechanical vibrations at frequencies between 1.0 and 3.0MHz. As the energy within the sound wave is passed to a material, it causes oscillation of the particles of that material thus generating heat. In addition to thermal changes, the vibration of the tissues may have a separate mode of action. Pulsed ultrasound has been recommended for acute pain and inflammation, and continuous ultrasound for the treatment of stiffness.

Low level laser therapy (LLLT) is a light source that generates extremely pure light, of a single wavelength. The effect is not thermal, but rather related to photochemical reactions in the cells. A study on meta-analysis revealed that the pooled results show no effect of 1 month of LLLT on pain or overall patient-rated assessment of disease activity. Lower dosage of LLLT was found as effective as higher dosage for reducing pain and improving knee range of motion (Brossea et al., 2004).

### **2.5.3.1c      *WEIGHT CONTROL***

Being overweight was the single most important potentially modifiable risk factor for development of lower limb osteoarthritis. It was also proven to reduce the risk of symptomatic knee osteoarthritis (Felson, 1992).

### **2.5.3.1d      *ORTHOTIC DEVICES***

Knee braces improved the proprioception and mechanical support of knee. This helped in pain relief by altered the mal-aligned motion of knee. Walking aids can reduce pain in patients with knee OA. Patients should be given instruction in the optimal use of a cane or crutch in the contra-lateral hand. Frames or wheeled walkers are often preferable for those with bilateral disease (Chan et al., 2005).

## **2.5.3.2      *PHARMOCOLOGICAL THERAPY***

### **2.5.3.2a      *ORAL DRUG THERAPY***

Non-steroidal anti-inflammatory drug(s) (NSAIDs) and Celebrex (celecoxib), COX-2 inhibitors have been shown to be equally effective in the symptomatic treatment of OA, but have no lasting effect after 2 years (Simon, Lanza et al., 1998). Compared to COX-2 inhibitors, the most important drawback of NSAIDs is the increased risk of upper gastrointestinal bleeding. Risk factors for upper gastrointestinal bleeding in patients treated with NSAIDs include age 65 or older, history of peptic ulcer disease or previous upper gastrointestinal bleeding, concomitant use of oral corticosteroids or anticoagulants and possibly smoking and alcohol consumption.

Additionally, the possible side-effects of these drugs and effect on cartilage metabolism should be taken into account as studies suggest that some NSAIDs, such as Naproxen, Ibuprofen and Indomethacin; inhibit matrix synthesis (Chen et al., 2007).

El Hajjaji et al. (2003) have shown that Celecoxib (COX-2-Inhibitor) has a beneficial effect on cartilage matrix metabolism. A consensus exists that the choice between NSAIDs and COX-2 inhibitors should be made based on the evaluation of risk factors for upper gastrointestinal bleeding, as to date COX-2 inhibitors are more expensive than most NSAIDs.

### **2.5.3.2b      NUTRITIONAL SUPPLEMENTS**

Public interest in the use of glucosamine for OA, gained momentum after the 1997 publication of 'The Arthritis Care' which described its ability to provide symptomatic relief with few side effects. Glucosamine is the hexosamine constituent of keratan sulphate, the glycosaminoglycan found in hyaline cartilage along with chondroitin sulphate. Glycosaminoglycans are the major constituents of proteoglycan molecules of hyaline cartilage. The proteoglycan moiety gives hyaline cartilage its visco-elastic property and allows it to act as a cushion.

Glucosamine and chondroitin sulphate are thought to influence cartilage metabolism as suggested by in-vitro models and animal studies. Proponents have promoted glucosamine and chondroitin sulphate as chondro-protective dietary supplements with matrix modifying properties. Both agents have more than one mechanism of action. They may stimulate production of cartilaginous matrix and down regulate the production of proteolytic enzymes. They may also improve synovial fluid characteristics and may have anti-inflammatory properties. It remains unclear as to whether these effects are physiologically significant

A Cochrane review (2005) of eight well-controlled studies failed to show benefit of glucosamine for pain and Western Ontario and McMaster Universities (WOMAC) function (Towheed et al., 2005). Collective analysis of 20 randomized control trials (RCTs) (including those without adequate allocation concealment) with 2570 patients found that glucosamine showed significant improvement in pain and over placebo. WOMAC outcomes did not achieve statistical significance. Reviews done at 6 weeks showed a decrease in pain and improved function, but studies reported at 3 months showed little difference. Two RCTs showed that a glucosamine preparation was able to slow radiological progression of OA of the knee over a 3-year period. However, the reliability of radiographic assessment of the progression of OA remains controversial (Mazzuca et al., 2004).

The reported minor side effects of glucosamine include gastro-intestinal complaints, headache, leg pain, edema, and itching. However, it is generally well tolerated (Hathcock et al., 2007). Evidence based on animal studies suggests that glucosamine may affect the metabolism of glucose and insulin and hence its use in diabetics may be restricted until human studies are available (Anderson et al. 2005); (Dostrovsky et al. 2011). Clegg, Reda, Harris, Klein, O'Dell, ... and Williams (2006) reported that combined treatment of glucosamine and chondroitin are significantly more effective in reducing pain than glucosamine and chondroitin sulfate alone in the intervention group over 24 weeks follow-up amongst 1583 patients ( $\geq 40$  years) with symptomatic knee OA (diagnosed with clinical evidence and radiographic evidence).

### **2.5.3.2c      VISCO- SUPPLEMENTATION**

Originally described by Balazs and Denlinger in the 1960s, it was first used (intravenously) to treat racehorses with traumatic arthritis. Hyaluronic acid is a component of normal synovial fluid and an important contributor to joint homeostasis. In OA, both the concentration and the molecular weight of hyaluronic acid are

decreased, which reduces the visco-elasticity of synovial fluid. The exact mechanism of action of visco supplementation is unclear.

The actual period that the injected hyaluronic acid stays within the joint space is in the order of hours to days, but the time of clinical efficacy is several months. Other postulated mechanisms to explain the long- lasting effect of visco- supplementation include possible anti-inflammatory and analgesic properties or stimulation of in-vivo hyaluronic acid synthesis by the exogenously injected hyaluronic acid.

Visco- supplementation involves the use of hyaluron and hylan derivatives. Hylans are cross- linked hyaluronic acids, which gives them a higher molecular weight and increased visco- elastic properties. The higher molecular weight of hylan is thought to make it elective and to make it reside longer in the joint space (i e., slower resorption).

The recommended injection schedule is one injection per week for 3 – 5 weeks for various commercial preparations although higher molecular weight preparations can be given as a single injection. Repeat courses of visco- supplementation can be performed after 6 months and are shown to be effective in patients who had a previous favorable clinical response. If effusion is present, aspiration of the joint is recommended before the injection to prevent dilution of the injected hyaluronic acid.

A meta-analysis (2004) on the therapeutic effects of hyaluronic acid on OA knee found significant improvements in pain and functional outcome. Patients older than 65 years of age and those with the most advanced radiographic stage of OA (complete loss of joint space) were found to be less likely to benefit from visco-supplementaion therapy (Wang et al., 2004).

A more recent Cochrane review (2005) also concluded that visco- supplementation is an effective treatment for OA of the knee with beneficial effects on pain, function and patient global assessment. The maximal improvement in symptoms occurred between 5 and 13 weeks following the injection (Bellamy et al., 2005).

## **2.6 PSYCHOLOGICAL FACTORS IN PERSISTENT PAIN**

Harris, Loxton, Sibbritt and Byles (2012) studied on the influences of psychosocial factors which contributed to arthritis burden. The findings from 10, 509 ageing cohort of Australian women revealed that women with arthritis had chronic stress perception, anxiety disorder and poor mental health. Therefore, interventions aimed at importance of psychological needs of women to improve general health are important.

A few studies have examined the relationships among self- efficacy, pain coping strategies, depression, pain intensity and outcomes in patients with chronic pain. Harrison (2004) has done a study on the influence of pathology, pain, balance and self- efficacy on the functional performance among women with osteoarthritis of the knee. Results revealed that pathology was not correlated with functional performance ( $p=0.27$ ). However, level of pain and self- efficacy in pain management

was correlated with functional self- efficacy and functional difficulty. Furthermore, functional self- efficacy was correlated with level of pain, functional difficulty and functional performance among women with osteoarthritis of the knee. Turner, Ersek and Kemp (2005) reported that self- efficacy in pain management was highly correlated with disability function, pain coping strategies and depression ( $p < 0.001$ ). However, self- efficacy in pain management was not statistically significant with pain intensity. Costa, Maher, McAuley, Hancock and Smeets (2011) determined that self- efficacy in pain management mediated the relationship between pain intensity and disability function among patients (mean age of 43 years) with acute low back pain in primary care.

## **2.7 COGNITIVE BEHAVIORAL THERAPY**

There were few studies have studied the effectiveness of the psychological intervention on knee osteoarthritis pain. However, cognitive- behavioral therapy (CBT) has become a first-line psychosocial treatment for individuals with chronic pain (Ehde, Dillworth, & Turner, 2014). A recent randomized controlled trial study done by Helminen et al. (2013) on the effectiveness of group cognitive behavioural intervention on knee osteoarthritis pain for the duration of 12 months follow- up had addressed the importance of cognitive behavioural therapy intervention to the current conservative treatment care for knee osteoarthritis related pain. However, cognitive behavioural therapy was not widely available for the treatment for knee osteoarthritis pain.

A randomized controlled trial study on the effectiveness of self- management education program based on social cognitive theory and cognitive behavioural therapy was carried out amongst 146 knee osteoarthritis patients. Results revealed that pain and functional disability were reduced significantly in intervention group as compared to control group over a six- months follow- up period (Coleman et al., 2012).

## **CHAPTER 3 METHODOLOGY**

### **3.0 STUDY LOCATION**

This study will be conducted at Orthopaedic Clinic in government hospital, namely Hospital Putrajaya and Hospital Serdang.

### **3.1 STUDY DESIGN**

This study is a 2 arm randomized clinical trial involving diagnosed knee osteoarthritis patients who are eligible to the study from February 2015 to July 2015 at Hospital Putrajaya and Hospital Serdang, Selangor, Malaysia, will be conducted. The sample population will be randomly divided into experimental and control groups by applying block randomization technique in a ratio 1:1. Random allocation will consider and eliminate the possible bias based on the socio- demographic characteristics of the patients. The experimental group will receive Cognitive Behavioral Treatment (CBT) provided with The Knee Book (Ministry of Health, 2013) added to standard routine care, whereas the control group will receive standard routine care only provided with The Knee Book and follow the same schedule of assessment as the experimental group. For standard routine care, patients need to attend their clinic and physiotherapy session as usual based on their fixed appointment date. A baseline measurement on patients' knee pain intensity, functional disability, psychological distress (depression, anxiety and stress), fear- avoidance beliefs, pain catastrophising and self- efficacy in pain management will be collected on respondents in both intervention and control group prior to the introduction of CBT. The efficacy endpoint will then be measured immediately, one month and six months after intervention. Figure 3.1 shows the schematic diagram of the study design.

[figure not shown]

Figure 3 Schematic diagram of the study design

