#### **1.4 RESEARCH HYPOTHESIS**

**H1:** There is no significant difference between the sociodemographic characteristics of patients enrolled at Orthopaedic Clinic in Hospital Serdang and Hospital Putrajaya

**H2:** The cognitive behavioral therapy module is effective in reducing knee pain intensity in patients with osteoarthritis of the knee.

**H3:** The cognitive behavioral therapy module is effective in reducing functional disability in patients with osteoarthritis of the knee.

**H4:** The cognitive behavioral therapy module is effective in reducing depression in patients with osteoarthritis of the knee.

**H5:** The cognitive behavioral therapy module is effective in reducing anxiety in patients with osteoarthritis of the knee.

[figure not shown]
**H6:** The cognitive behavioral therapy module is effective in reducing stress in patients with osteoarthritis of the knee.

**H7:** The cognitive behavioral therapy module is effective in reducing fear- avoidance beliefs in patients with osteoarthritis of the knee.

**H8:** The cognitive behavioral therapy module is effective in reducing pain catastrophising in patients with osteoarthritis of the knee.

**H9:** The cognitive behavioral therapy module is effective in improving self- efficacy in pain management in patients with osteoarthritis of the knee.

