### **3.6 SAMPLING FRAME**

A list of all patients with knee osteoarthritis seen at orthopaedic clinic of each recruitment site (obtained from the medical records department of each hospital).

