### **3.8 SAMPLING METHOD**

#### **Randomization and Masking**

The participants will be recruited from Hospital Putrajaya and Hospital Serdang. Participants will be identified from physician and from searches of patient records

that had consulted for knee pain problem within the period of February 2015 to July 2015. Patients will be invited to give consent to be contacted by staff nurse for the permission to review patients' medical records for a diagnosis of knee osteoarthritis. Patients of each recruitment site who were eligible will be contacted by researcher to enquire their willingness to participate in this research study. Potentially eligible patients will be invited to attend a face-to-face appointment with a researcher to discuss participating in the trial and to confirm their eligibility. Ineligible patients (and those who declined participation) will be referred back to their general practitioner. Those eligible patients who agreed to participate in this study will be in a list and numbered. The number in the name list of all eligible knee osteoarthritis patients who were agreed for the participation will be randomly chosen by using draw logs until 300 names been obtained from the list, in order to ensure that no bias will be involved in patient recruitment.

The selected 300 names from the sampling frame will be randomly allocated to either of the experimental or control group based on block randomization method by using random allocation software after the written consent obtained and baseline questionnaire administered. Then, the names will be divided into 13 smaller subgroups (eight to ten each subgroup) in each intervention and placebo group. All the names in the subgroups will be contacted personally before every assignment by a hospital staff who will be blinded to group allocation.

Because of the nature of the treatments, the participants or those providing the interventions to treatment assignment will be unable to mask. However, research assistants who obtained and assessed outcomes will be masked to assignment. Besides, the research assistants for treatment and control group are different. The research assistants then will submit the outcome measurements at each time measure to the researcher who is undertaking the analysis task.

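### The protocol says allocation removes socio-demographic bias, but the block randomisation described uses no patient characteristic and no stratification by hospital, so balance holds only on average

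*Protocol*

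**What the plan says.** Protocol 3.1 describes the sample as "randomly divided into experimental and control groups by applying block randomization technique in a ratio 1:1" and then makes the balance claim: "Random allocation will consider and eliminate the possible bias based on the socio- demographic characteristics of the patients".

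Protocol 3.8 (Randomization and Masking) gives the steps. "The participants will be recruited from Hospital Putrajaya and Hospital Serdang". "Those eligible patients who agreed to participate in this study will be in a list and numbered". Names are drawn from that list until 300 are obtained, and these are "randomly allocated to either of the experimental or control group based on block randomization method by using random allocation software". The Procedures part of 3.8 repeats that block randomisation is used and adds that a person outside recruitment carries it out, so that allocation is concealed.

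None of these places names a stratification factor, a minimisation scheme or a block size. None says whether the list or the blocks are kept separate by hospital.

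Hospital does appear elsewhere. The sampling frame in 3.6 comes from each site's records, and the first hypothesis in 1.4 concerns the two sites: "There is no significant difference between the sociodemographic characteristics of patients enrolled at Orthopaedic Clinic in Hospital Serdang and Hospital Putrajaya". Hospital is not among the covariates in 1.5 (age, gender, obese status) or the independent variables in 3.9.

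**The concern.** The sentence in 3.1 credits the allocation with something the described method does not do. Permuted blocks keep the numbers in the two arms close. They use no information about the patient, so age, gender, ethnicity, income and hospital fall as chance puts them. To take such characteristics into account, the scheme would have to stratify or minimise on named factors.

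Two things are at stake. First, a reader of 3.1 may believe that balance on patient characteristics is built into the design, and may see no need to stratify or adjust. Second, hospital is the one factor that is known for every patient, has only two levels and costs almost nothing to stratify on. Without it, some chance imbalance between hospitals can enter the primary comparison of knee pain. Stratification cannot be added once patients have been allocated, so a later statistical analysis plan cannot supply it.

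**Working it through.** **Inputs from the protocol.** Knee pain standard deviation 10.85, means 20.68 and 16.54 (difference 4.14), effect size 0.38, z values 1.96 and 0.842, 20% attrition (3.5); 1:1 allocation (3.1); 300 names and two hospitals (3.8).

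**Assumptions, because the protocol is silent.** The share of patients from one hospital is taken as 50%, with 30:70 as an alternative. The numbered list is taken to mix the two hospitals.

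**1. The protocol's own figure.** n per group = 2(1.96 + 0.842)² / 0.38² = 15.70 / 0.1444 = 108.7, so 109, as stated. The unrounded inputs give 2 × 10.85² × 2.802² / 4.14² = 107.9, so 108, which agrees within rounding. Attrition: 109 × 1.2 = 130.8, so 131 per group and 262 in total, as stated. Section 3.8 allocates 300, so both totals are used below.

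**2. Chance imbalance in hospital.** With N patients, half in each arm and K from one hospital, the number of that hospital's patients in the CBT arm is hypergeometric.

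- N = 262, K = 131: variance = 131 × 0.5 × 0.5 × 131/261 = 16.4, standard deviation 4.05. The 95% range is 58 to 73 around 65.5.
- The between-arm difference in hospital share is 2(x − 65.5)/131, with standard deviation 2 × 4.05/131 = 6.2 points.
- N = 300, K = 150: variance = 150 × 0.25 × 150/299 = 18.8, standard deviation 4.34. In share, 2 × 4.34/150 = 5.8 points.

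| N | Split | SD of share difference (points) | Probability of about 10 points or more |
|---|---|---|---|
| 262 | 50:50 | 6.2 | 8.3% |
| 262 | 30:70 | 5.7 | 5.9% |
| 300 | 50:50 | 5.8 | 8.3% |
| 300 | 30:70 | 5.3 | 5.8% |

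In all four cases a difference above 20 points has probability 0.13% or less. Simulating permuted blocks of 4 and of 10 on a mixed list of 300 gives standard deviations of 5.7 and 5.8 points and a mean difference of essentially zero. Blocking therefore leaves hospital to chance, without favouring either arm.

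**3. If the list were sorted by hospital.** The same simulation gives a standard deviation of 0.8 points or less. Hospital would then be nearly balanced, but the protocol does not ask for this ordering.

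**4. What it could mean for the estimate.** Suppose the hospitals differed by 0.5 SD in outcome (an assumption; the protocol gives no such figure). A 10-point imbalance would move the estimate by 0.10 × 0.5 = 0.05 SD. The standard error with 131 per arm is √(2/131) = 0.124 SD, so the shift is 0.05/0.124 = 0.4 standard errors. With a 50:50 split, hospital would then account for 0.5 × 0.5 × 0.5² = 0.0625 of the variance. Removing it would shrink the standard error by 1 − √0.9375 = 3%.

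**The case against.** The strongest reply is that the sentence in 3.1 speaks of bias, and randomisation does remove systematic bias from patient characteristics. On that reading it is clumsy but not false, and chance imbalance is already reflected in the standard error. The second half of this stands: there is no bias here, and the loss is one of precision. The first half does not rescue the sentence, because it says that allocation takes the characteristics into account, and no step described does so.

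A second reply is that an analysis adjusting for hospital would recover most of the precision even without stratification, and that an analysis plan not shown here might specify it. This is largely right. At a 50:50 split, a 10-point imbalance inflates the variance of an adjusted comparison by only 1/(1 − 0.10²) = 1.01. It limits the size of the point, but stratification itself still has to be settled in the protocol before allocation.

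Several stronger readings may tempt a reader, and the documents do not support them.

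- *That the protocol specifies one pooled sequence.* This is inferred from the single numbered list and the absence of any stratifier; it is not stated.
- *That hospital is left unbalanced.* It is balanced in expectation.
- *That hospital determines routine care.* Sections 3.1 and 3.11 say only that patients keep their usual clinic and physiotherapy appointments.
- *That the first hypothesis shows the hospitals differ.* It is worded as no difference and concerns socio-demographic characteristics, not pain.
- *That CBT groups of eight to ten could not be filled at each hospital.* Any count from 58 to 70 splits into seven groups (56 to 70), and 71 to 73 into eight (64 to 80).

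**Conclusion.** The point holds at modest size. The balance claim in 3.1 does not match the method in 3.1 and 3.8, which controls arm totals and nothing else. This follows from the text and needs no assumption.

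The effect for hospital rests on an assumed split and on a list that mixes the sites: a standard deviation of about 6 percentage points in the between-arm difference, with 10 points reached in about 8% of randomisations (about 6% at 30:70). The result is a small, avoidable loss of precision.

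A reader might divide the 0.05 SD shift by the planned 0.38 and report a bias of 13%. That would be wrong. The 0.5 SD hospital difference is assumed, the imbalance lies in the tail, and the shift is chance error of about 0.4 standard errors that averages to zero over randomisations.

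**What to change.** In 3.1 and 3.8, specify a separate 1:1 permuted-block list for each hospital, generated before the first allocation, and include hospital as a factor in the outcome comparison. Replace the balance sentence in 3.1 with a statement that allocation is stratified by hospital and that other characteristics are balanced only on average.

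The cost is two lists instead of one, from the allocation software already planned, plus a line of wording. The sample size stays at 109 per group, 131 after the stated attrition. Imbalance in hospital then falls to at most about half a block per site. If the sponsor prefers not to stratify, the sentence in 3.1 should still be corrected.
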